ICH	International Conference on Harmonisation of Technical Requirements for Registration of Pharmaceuticals for Human Use
Ig	Immunoglobulin
IM	Intramuscular
MedDRA	Medical Dictionary for Regulatory Activities
N	Number (typically refers to participants)
PI	Principal Investigator
PP	Per Protocol
PS	Polysaccharide
PT	Preferred Term
SAE	Serious adverse event
SAP	Statistical Analysis Plan
SD	Standard deviation
SOC	System Organ Class
ULN	Upper limit of normal
USA	United States of America
WBC	White blood cells
WHO	World Health Organization

1 PREFACE

The Statistical Analysis Plan (SAP) for "Safety, Tolerability and Immunogenicity of a new *Enterotoxigenic Escherichia coli* Vaccine (ETVAX) containing 4 different inactivated *E. coli* strains and a hybrid LCTBA protein, given alone and together with different doses of dmLT adjuvant in descending age-groups" describes and expands upon the statistical information presented in the PATH protocol OEV-122/VAC-014.

This document describes all planned analyses and provides reasons and justifications for these analyses. It also includes sample tables, listings, and figures planned for the final analyses. Regarding the final analyses and Clinical Study Report (CSR), this SAP follows the International Conference on Harmonisation of Technical Requirements for Registration of Pharmaceuticals for Human Use (ICH) Guidelines, as indicated in Topic E3 (Structure and Content of Clinical Study Reports), and more generally is consistent with Topic E8 (General Considerations for Clinical Trials) and Topic E9 (Statistical Principles for Clinical Trials). The structure and content of the SAP provides sufficient detail to meet the requirements identified by the Food and Drug Administration (FDA) and ICH, while all work planned and reported for this SAP will follow internationally accepted guidelines published by the American Statistical Association and the Royal Statistical Society for statistical practice.

This document contains four sections: (1) a review of the study design, (2) general statistical considerations, (3) comprehensive statistical analysis methods for efficacy and safety outcomes, and (4) a list of proposed tables and figures. Any deviation from this SAP will be described and justified in protocol amendments and/or in the CSR, as appropriate. The reader of this SAP is encouraged to also review the study protocol for details on conduct of the study and the operational aspects of clinical assessments.

2 INTRODUCTION

The global diarrheal disease burden remains high with approximately four billion cases estimated to occur annually in all age groups, with the highest incidence among infants and younger children under five years of age. In this age group, enteric infections result in nearly 600,000 deaths each year and extract an enormous physical and economic toll in low-resource countries. Large projects have been developed to combat many of the sanitation and malnutrition needs of the populations living within ETEC endemic areas. While these projects have been associated with a lowering of diarrhea episodes within those regions, incidence rates remain high and have changed very little. In ETEC endemic areas it has been estimated that infants and younger children may experience between two to five symptomatic diarrhea episodes due to ETEC within the first three years of life. Currently ETEC is the most important pathogen, among the primary infectious causes of diarrheal disease, for which there is currently no licensed vaccine.

ETEC has long been a WHO target for vaccine development and remains a WHO priority. The information gained from experimental and clinical studies of the 1st generation vaccine, containing ETEC bacteria expressing common colonization factors mixed with cholera toxin B subunit, suggests that a vaccine formulation containing increased amounts of CF antigens may induce stronger levels of anti ETEC immunity and better protective efficacy. A successful phase I trial in Sweden supports further evaluation of the safety and immunogenicity of ETVAX among younger age-groups in an ETEC endemic area.

This phase I/II clinical study is designed to evaluated the safety, tolerability and immunogenicity of the study vaccine. The study will first test the vaccine with and without dmLT in healthy adults, and then move sequentially into toddlers (24-59 months old), younger children (12-23 months old), and infants (6-11

months old). All participants will receive two oral doses of ETVAX with or without dmLT adjuvant or placebo. Prior to moving to the next age group available safety data will be evaluated and reviewed by the International Centre for Diarrheal Disease Research, Dhaka, Bangladesh (icddr,b) DSMB, after which a recommendation will be made on whether to proceed to the next age group.

2.1 Purpose of the Analyses

This Phase I/II trial will serve to assess whether ETVAX is safe and provides mucosal as well as systemic immune responses against the key protective antigens when tested in different age-groups in Bangladesh. This study provides an opportunity to test the safety profile of a mucosal adjuvant, double-mutant LT (dmLT), in adults and children, as well as provides the opportunity to potentially assess the ability of dmLT to further enhance the mucosal and systemic antibody responses to key antigens in the ETVAX vaccine among age groups in developing country sites, like Bangladesh, that have proved refractory to oral immunization with enteric vaccines. In addition, this study also allows for the evaluation of the potential dose-sparing effect of dmLT when combined with a lower dose of vaccine. Finally, this clinical trial is considered an essential study along the critical path of the overall clinical development plan before determining whether the vaccine can be tested for protective efficacy in children in developing countries.

3 STUDY OBJECTIVES AND ENDPOINTS

3.1 Study Objectives

3.1.1 Primary Objective

The primary objective deals with safety and tolerability and is the following:

• To evaluate the safety and tolerability of orally administered ETVAX, containing 4 different inactivated *E. coli* strains over-expressing CFA/I, CS3, CS5 and CS6 and a hybrid LCTBA protein, given along and together with different dosages of dmLT adjuvant in descending age groups in Bangladesh.

3.1.2 Secondary Objective

The secondary objectives deal with immunogenicity and are the following:

- To assess vaccine induced IgA antibody responses in lymphocyte secretions by the ALS assay against LTB, CFA/I, CS3, CS5 and CS6 in descending age-groups
- To evaluate vaccine induced fecal secretion IgA (SIgA) antibody responses against CFA/I, CS3, CS5, CS6, O78 LPS and LTB in applicable age-groups in Bangladesh
- To assess vaccine induced plasma IgA antibody responses against LTB, O78 LPS, CFA/I, CS3, CS6 and CS5 and IgG antibody responses against LTB and O78 LPS
- To evaluate vaccine induced ALS IgA responses against O78 LPS (if sample volume allows)
- To assess adjuvant effect of dmLT on vaccine immune response compared to responses when giving vaccine alone in descending age-groups in Bangladesh

3.2 Endpoints

3.2.1 Primary Endpoints

The primary endpoints deal with safety and tolerability and are the following:

- Proportion (%) of SAEs
- Proportion (%) of AEs
- Proportion (%) of vaccine induced reactogenicity events

3.2.2 Secondary Endpoints

The secondary endpoints deal with immunogenicity and are the following:

- Antibody response (>two-fold increase in antibody titers between baseline and post-immunization),
 Geometric Mean Titer (GMT), and Geometric Mean Fold Rise (GMFR) between baseline and post-immunization to CFA/I, CS3, CS5, CS6 and LTB as measured by ALS IgA
- Antibody response (>two fold increase in antibody titer between baseline and post-immunization),
 GMT, and GMFR to CFA/I, CS3, CS5, CS6 and LTB as measured by fecal SIgA
- Antibody response (>two-fold increase in antibody titers between baseline and post-immunization),
 GMT, and GMFR to CFA/I, CS3, CS5, CS6 and LTB as measured by plasma IgA
- Antibody response (>two-fold increase in antibody titers between baseline and post-immunization),
 GMT, and GMFR to LTB and O78 LPS as measured by plasma IgG
- Antibody response (>two-fold increase in antibody titers between baseline and post-immunization),
 GMT, and GMFR to O78 LPS as measured by ALS IGA, fecal SIgA, and/or plasma IgA

3.2.3 Exploratory Endpoints

The exploratory endpoints deal with immunogenicity and are the following:

- T cell immune responses (proliferation and/or cytokines as measured by flow cytometry)
- Neutralizing antibody geometric mean titers (GMT)
- Avidity of immune responses
- Immunoproteomic profile of vaccine induced antibody responses in plasma or intestinally derived samples

3.3 Study Definitions and Derived Variables

The following definitions and derivations will be used in this study:

 Diarrhea is defined as ≥ 3 unformed or loose stools (mixed liquid and solid components) in a 24 hour period or at least 1 bloody loose or liquid stool or 1-2 liquid stools with at least some dehydration.

- 2. If a participant meets the definition of diarrhea, the start of the diarrhea episode will be the time of the first unformed stool which contributes to meeting the definition and the end of the diarrhea episode will be the time of the last unformed stool. If there is greater than 24 hours between loose or unformed stools then the illness will stop and a new AE will begin.
- 3. Mild diarrhea is defined as at least 3 looser than normal stools without dehydration in a 24 hour period.
- 4. Moderate diarrhea is defined as at least 3 looser than normal stools with dehydration in a 24 hour period.
- 5. Severe diarrhea is defined as at least 3 looser than normal stools with severe dehydration.
- 6. The baseline value will be defined as the last value obtained prior to the first vaccination of study product.
- 7. The reference day will be the day of the first vaccination and will be referred to as Day 1.
- 8. Study days prior to vaccination will be dependent upon the first dose of the vaccine. If the assessment occurred prior to the first dose, study days will be calculated by taking the date minus the first vaccination date (reference day).
- 9. Study days occurring on or after the date of vaccination will be dependent upon when the assessment occurred. If the assessment occurred on or after the first vaccination but prior to the second vaccination, study days will be calculated by taking the date minus the first vaccination date (reference day) and adding 1. If the assessment occurred on or after the second vaccination, then study days will be calculated by taking the date minus the second vaccination date and adding 1.
- 10. Age will be calculated from the date of enrollment and will be presented in whole years for adults and in months for children under 5 years of age (truncated integer).
- 11. The calculations for GMTs will be performed by taking the anti-log of the arithmetic mean of the log₁₀-transformed titers.
- 12. Fold increase/rise will be calculated as the following:
 - a. For fold rise compared to baseline: ratio of: $\frac{post-immunization\ titer}{pre-immunization\ titer}$
 - b. For fold rise of post dose 1 compared to post dose 2: ratio of: $\frac{post\ dose\ 2\ titer}{post\ dose\ 1\ titer}$
- 13. The calculations for geometric fold rises (GMFR) will be performed by taking the anti-log of the difference in log-transformed titers.
- 14. Antibody response is defined as ≥ two-fold increase in GMFR antibody titers between baseline (pre-immunization titer) and post immunization titer.
- 15. Prior medications are those medications that started and stopped prior to vaccination.

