6.5 Missing Data

In general, all missing data will be treated as missing completely at random and no imputation will be performed except for the safety endpoints as described below. Non-analyzable data (e.g., due to major protocol violations) will be documented in the deviations.

If some safety data are available for a participant in the FA population, but respective secondary endpoint related data are missing, then the participant will be included in the safety analysis and data will be treated as follows for immediate AEs, unsolicited AEs and serious adverse events (SAEs).

- 1. If Severity is missing for any AE, then it will be considered as an AE of maximum severity (Grade 3) "Severe", unless it is captured as SAE.
- 2. If "Relationship" is missing, then it will be considered as "Related" to the vaccine administered.
- 3. If, for Start date, the day of event/condition is missing due to any adverse event, then it will be imputed as the date of last dose of study vaccine.
- 4. If the Stop date of an adverse event is missing, then it will be treated as ongoing.

For solicited adverse events, the following assumptions will be made:

- 1. If dates are missing, but symptoms are reported, then the day post vaccination will be used to calculate the date of the symptom.
- 2. If a symptom is not reported at any time through Day 7, then no imputation for missing data will be performed. The data will be summarized as not reported on the tables.

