6.6.2 Study Pause

Study pause is defined as a decision to cease, temporarily or definitely, enrollment and all vaccinations. Study pause or final cessation of vaccinations will not eliminate any safety follow-up procedures specified by the protocol. The Sponsor will pause vaccinations in the study if the IPST, DSMB or protocol team including the PATH Medical Officer and Emmes Medical Monitor, determines that study hold criteria have been met, or in the event of any other safety concerns.

The following study pause rules will automatically pause or halt further vaccinations until the protocol team consisting of the PI, study physician, independent medical monitor, PATH Medical Officer and Emmes Medical Monitor, has performed a review. However participants already enrolled will continue to be followed for safety during the pause. These pause rules refer to suspected adverse reactions and will be triggered automatically if any of the events described below are met during the conduct of the study:

- One participant death from Day 0 to Day 42, unless judged definitely unrelated to vaccination;
- One participant with a serious AE (SAE) judged as definitely or probably related to vaccine;
- >2 participants in a cohort with the same ≥ grade 3 (severe) solicited AE within three days following vaccination judged as definitely or probably related to vaccine;
- >2 participants in a cohort with the same \geq grade 3 (severe) abnormal clinical monitoring laboratory value (7 days following vaccination) judged as definitely or probably related to vaccine;
- >2 participants in a cohort with the same ≥ grade 3 (severe) AE judged as definitely or probably related to vaccine.

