9.1.1 Solicited Events and Symptoms

Solicited adverse events will be collected pre-vaccination, 60 minutes post-vaccination and then daily for 7 days after vaccination and graded on a scale of 0 (absent), 1 (mild), 2 (moderate) and 3 (severe). Solicited events include: elevated oral temperature, nausea, vomiting, loose stools, diarrhea, abdominal pain/stomach ache, and acute systemic allergic reaction. Adults will have all events collected. Toddlers (24 - 59 months) will have all events except nausea collected and Younger Children (12 - 23 Months) and Infants (6 - 11 months) will only have oral temperature, vomiting, loose stools, diarrhea and acute systemic allergic reaction collected.

The proportion of participants reporting at least one solicited adverse event within 7 days of any vaccination will be summarized for each solicited adverse event and for any solicited adverse event. The 95% CI calculated using Clopper-Pearson methodology from a binomial distribution (SAS Proc Freq with a binomial option) will be presented (Tables 14.3.1.1(a)(b)(c)(d)).

For each solicited adverse event and for any solicited adverse event, the maximum severity over 7 days after each vaccination will be summarized for the Safety population. The number and percentage of participants reporting each event will be summarized for each treatment group by the maximum severity. For each event the denominator is the number of participants with non-missing data for the specific event (Tables 14.3.1.2(a)(b)(c)(d)).

The number and percentage of participants reporting any solicited adverse event and reporting each individual solicited adverse event will be summarized for each day post vaccination for each vaccination by Treatment group (Tables 14.3.1.3(a)(b)(c)(d)) and severity. The percent of participants reporting any solicited event will be displayed graphically in a bar chart in Figures 14.3.1.4(a)(b)(c)(d)).

Fisher's exact test will be used to compare the proportion of participants with solicited reactogenicity events between each of the vaccine arms with the placebo arms. In addition, the vaccine arms without dmLT will be combined, the vaccine arms with dmLT will be combined and all vaccine arms will be combined and each will be compared to placebo. The results will be summarized in Tables 14.3.1.5(a)(b)(c)(d).

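### Section 3.3 admits diarrhoea with fewer than 3 stools but gives it no severity grade, and its moderate and severe grades overlap

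*SAP*

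**What the plan says.** Section 3.3, item 1, starts with the stool-count route, "Diarrhea is defined as ≥ 3 unformed or loose stools (mixed liquid and solid components) in a 24 hour period", and then adds two alternatives: "or at least 1 bloody loose or liquid stool or 1-2 liquid stools with at least some dehydration".

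Items 3 to 5 of the same list set the grades:

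- "Mild diarrhea is defined as at least 3 looser than normal stools without dehydration in a 24 hour period"
- "Moderate diarrhea is defined as at least 3 looser than normal stools with dehydration in a 24 hour period"
- "Severe diarrhea is defined as at least 3 looser than normal stools with severe dehydration"

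The list is introduced as the set of definitions to be used in the study.

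Section 9.1.1 makes diarrhoea a solicited event in all four age groups, graded 0 to 3. For each solicited event, "the maximum severity over 7 days after each vaccination will be summarized for the Safety population", with participants who have non-missing data for that event as the denominator. The shells for Tables 14.3.1.2 have four rows per symptom: none, mild, moderate and severe. The daily shells, Tables 14.3.1.3, add a row for not reported. Tables 14.3.1.1 and 14.3.1.5 count participants with the event and do not use its grade.

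Section 6.5 sets a missing severity to Grade 3, but in a list confined to immediate AEs, unsolicited AEs and SAEs, and with an exception for events captured as SAEs. The separate list for solicited events covers missing dates and symptoms not reported. It has no severity rule.

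**The concern.** The case definition and the grading scale do not cover the same set of cases. The two routes that admit a participant with fewer than 3 stools are the ones that involve blood or dehydration, and these are the presentations that the scale leaves out.

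Reactogenicity is one of the three primary endpoints, and its severity breakdown is how tolerability by dose and adjuvant level will be read. A programmer who meets an ungraded case has no rule. The participant could be left out of the table, placed in the none row or graded ad hoc. Each choice gives a different severity distribution, and the severity table may then disagree with the incidence table on how many participants had diarrhoea. With 15 vaccinees per dose group in adults, toddlers and younger children, and 30 in infants (section 5), one participant moves a percentage by about 6.7 points (1/15) or 3.3 points (1/30).

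**Working it through.** The plan gives no figure to reproduce. The check is whether each case that meets item 1 has exactly one grade under items 3 to 5.

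**Inputs** (section 3.3, items 1, 3, 4 and 5). Stools in 24 hours: 1, 2, 3 or 4. Stool type: loose or liquid. Blood: no or yes. Dehydration: none, some or severe. That is 4 × 2 × 2 × 3 = 48 combinations.

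**Cases that meet item 1**

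- 3 or 4 stools: 2 × 2 × 2 × 3 = 24, all by stool count.
- 1 or 2 stools with blood: 2 × 2 × 3 = 12.
- 1 or 2 liquid stools, no blood, some or severe dehydration: 2 × 2 = 4.
- Total: 24 + 12 + 4 = 40. The other 8 do not qualify: 6 with 1 or 2 loose stools and no blood, and 2 with 1 or 2 liquid stools, no blood and no dehydration.

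**Grades available to them**

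| Case | Combinations | Grade under items 3 to 5 |
|---|---|---|
| 3 or more stools, no dehydration | 8 | mild |
| 3 or more stools, some dehydration | 8 | moderate |
| 3 or more stools, severe dehydration | 8 | moderate and severe |
| 1 or 2 stools with blood | 12 | none |
| 1 or 2 liquid stools, no blood, with dehydration | 4 | none |

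So 12 + 4 = 16 of 40 have no grade. Of these 16, severe dehydration is present in 2 × 2 = 4 with blood and in 2 without, making 6. All 24 cases with 3 or more stools can be graded, including those with blood. The 8 double-graded cases arise because item 4 asks for dehydration without excluding severe dehydration.

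**Does another rule supply the grade?** Take two liquid stools with some dehydration.

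- *Onset on day 3:* a solicited event. The solicited list in section 6.5 has no severity rule, and the not-reported provision concerns symptoms that were not reported. No grade follows.
- *Onset on day 9:* section 4.5.1 records a symptom that starts more than seven days after vaccination as an AE. If its severity is missing and it is not captured as an SAE, section 6.5 makes it Grade 3.

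The same presentation is thus ungraded on one date and severe on another. In both cases the event is reported somewhere. What the SAP does not define is where the day 3 case sits in Tables 14.3.1.2.

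**The case against.** The strongest reply is that the site assigns the grades. Section 4.5.1.2 says so and points to Protocol Appendix II for the criteria. Section 4.5.1.1 describes a graded scale based on function or size of reaction. On that view a grade will be in the data, and items 3 to 5 need not cover every case. This stands in part: whether such cases were left ungraded at the site cannot be settled from the SAP, because the appendix is not shown. It does not remove the problem. If the appendix grades these cases, it conflicts with items 3 to 5 and the SAP does not say which governs. If it repeats items 3 to 5, the gap is real.

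Other points limit how far the finding reaches.

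- A reader might infer that these events drop out of the safety reporting. They do not: the incidence tables count them, and loose stools is a separate solicited event with its own severity rows.
- A reader might infer that any bloody stool is ungradable. That holds only with fewer than 3 stools in 24 hours.
- A reader might infer that the pause rule in section 6.6.2 fails, since it counts Grade 3 or higher events of the kind "solicited AE within three days following vaccination judged as definitely or probably related to vaccine". The documents do not support that. Whether the site could call such a case Grade 3 depends on Appendix II. The triggers for a death and for a related SAE need no grade, and the sponsor may pause for any other safety concern. The rule needs more than 2 participants in a cohort, and cohorts number 25 (toddlers, younger children), 40 (infants) and 45 (adults), placebo included (section 4.3).
- Section 4.4.2 of this version lists the highest safe doses as already chosen, so rewording the SAP cannot change those decisions.

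The overlap between moderate and severe is the lesser fault. Most readers would settle it upwards in a maximum-severity table, but the text does not say so.

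**Conclusion.** The point holds as a contradiction within section 3.3. Item 1 admits cases with fewer than 3 stools, items 3 to 5 grade only cases with at least 3, and the top two grades overlap. In logical terms 16 of 40 qualifying combinations have no grade and 8 have two. The plan gives nothing from which to estimate how many participants that would be, and the number may be small.

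The practical effect is on final reporting. Solicited diarrhoea of this kind has no defined place in Tables 14.3.1.2, while Tables 14.3.1.1 and 14.3.1.5 include it. The incidence part of the primary endpoint is not affected. Any effect on the Grade 3 pause criterion is secondary and unproven.

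The conclusion assumes that section 3.3 governs the derivation of diarrhoea severity for the tables. The contrast with onset after day 7 also assumes that the severity rule in section 6.5 is applied generally to unsolicited AEs, although its lead-in sentence ties it to participants with missing secondary-endpoint data. The correction should be made before the severity tables are programmed.

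**What to change.** Reconcile items 1, 3, 4 and 5 of section 3.3 with each other and with Protocol Appendix II, so that every case meeting item 1 maps to exactly one grade, and state which source governs if they differ. The sponsor and medical monitor set the grades. No particular clinical grade is proposed here. Apply that mapping in Tables 14.3.1.2 and 14.3.1.3, and check that the mild, moderate and severe counts for diarrhoea in Tables 14.3.1.2 add up to the counts in Tables 14.3.1.1.

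The cost is a few lines of SAP text and one programming check. Item 1 already depends on stool count, blood and dehydration, so no new data should be needed, provided that the case report form holds them by day (it is not shown). If the agreed mapping differs from a grade that the site has already assigned, the SAP should say which one is tabulated.
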